3.4 Study Duration, Enrollment and Number of Sites

3.4.1 Duration of Study Participation

The study duration per subject will be about 180 days, with up to 1 day for screening (which coincides with the first day of phase 1), about 90 days for Phase 1, about 90 days for Phase 2, and 1 day for follow-up (which coincides with the last day of phase 2).

3.4.2 Total Number of Study Sites/Total Number of Subjects Projected

The study will be conducted at up to 6 investigative sites in the United States, the main CHOP Diabetes and Endocrinology outpatient clinic at the Buerger Center in Philadelphia PA; CHOP Specialty Care in Princeton, NJ; CHOP Specialty Care & Surgery Center in Chalfont, PA; CHOP Specialty Care & Surgery Center in King of Prussia, PA; CHOP Specialty Care & Surgery Center in Voorhees, NJ; and CHOP Specialty Care in Lancaster, PA.

Recruitment for randomized controlled trial will stop when 200 subjects are enrolled.
Recruitment for focus groups will stop when 50 subjects are enrolled.

3.5 Study Population

3.5.1 Inclusion Criteria

- 1) Males or females age 12 to 18 years.
- 2) Have a diagnosis of T1DM for more than 1 year.
- 3) HbA1c \geq 8% but $<$ 14%.
- 4) Have been in seen in the diabetes clinic in the last 6 months.
- 5) Own a personal mobile device with unlimited text messaging plan.
- 6) Parental/guardian permission (informed consent) and, if appropriate, child assent.

3.5.2 Exclusion Criteria

- 1) Subject is non-English speaking.
- 2) Subject has a significant cognitive disability or major organ illness.
- 3) Subject has hemolytic anemia.
- 4) Participation in the focus groups.
- 5) Ongoing steroid use

Subjects that do not meet all of the enrollment criteria may not be enrolled. Any violations of these criteria must be reported in accordance with IRB Policies and Procedures.

4 STUDY PROCEDURES

4.1 Pre-Intervention Phase: Focus Groups

Focus group will be recorded and transcribed. No identifying information will be collected.

4.2 Screening Visit (Visit 1)

Screening will take place just prior to Phase 1. It will consist of explaining the study and screening for eligibility. Subjects that qualify and are interested will move on to Phase 1

4.3 Study Treatment Phase

4.3.1 Visit 1

- Informed Consent and/or Subject Assent
 - Medical Record Review
 - Lab: hemoglobin A1c
-

- Registration on MyDiaText website by study staff
- SCI questionnaire

4.3.2 Visit 2

- Medical Record Review
- Lab: hemoglobin A1c
- SCI questionnaire

4.3.3 Visit 3

- Medical Record Review
- Lab: hemoglobin A1c
- SCI questionnaire
- Exit questionnaire

4.3.4 Assessment of adherence to program (Ongoing)

- Every two weeks, MyDiaText will report consecutive response to text message by subject number. If one subject has the longest streak, they will be rewarded with \$10 placed on their bank card. If more than one subject has the longest streak, MyDiaText will pick one subject at random to receive this reward. They will be informed if they received this reward via text message.

4.4 Unscheduled Visits

Since study visits will coincide with visits with primary diabetes provider, no unscheduled visits will take place. If a subject is seen by their diabetes provider or care team less than 2 months from the previous visit, then the study team will not approach the subject at that time.

4.5 Subject Completion/Withdrawal

Subjects may withdraw from the study at any time without prejudice to their care. They may also be discontinued from the study at the discretion of the Investigator for lack of adherence to study treatment or visit schedules. The Investigator may also withdraw subjects who violate the study plan, or to protect the subject for reasons of safety or for administrative reasons. It will be documented whether or not each subject completes the clinical study.

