3.2.1 Screening Phase

Potential subjects will be recruited from the CHOP Endocrinology and Diabetes outpatient clinic. Clinic schedules will be reviewed for determination of potential subjects as per the inclusion criteria above. Some subjects will be pre-screened for interest only, without eliciting PHHI, by telephone prior to their clinic visit. Subjects will be approached during their clinic visit and informed about the current study. If the subject agrees to participate, informed consent (from caregiver if subject is < 18 y/o and from subject if he/she is >18 y/o) as well as assent if subject is < 18 y/o will be obtained. HbA1c and diabetes treatment plan will be collected from the medical record.

3.2.2 Phase 1

This phase will start enrollment. Subjects will be registered into the MyDiaText website by research staff. At registration, MyDiaText will randomize half of the subjects to the intervention group and the other half to the control group. At this time, SCI will be administered via a text message link to the MyDiaText website; this will serve also to ensure the phone number for the patient was entered correctly and that account is active for log-in. All subjects will get \$5 upon completion of baseline self-care inventory. All subjects, control and intervention, will create a profile in the MyDiaText system. This profile will consist of his/her name, birthday, gender, ethnicity, phone number, and email. All subjects will be following their diabetes care plan as dictated by their primary diabetes provider. The subjects in the intervention group will start receiving the text messaging intervention as described in the intervention section (section 7). Subjects in the intervention group will be instructed to respond to each text as a proxy for having read it. Previously, a point system reflected scoring on quizzes and educational activities. To update the text messages based on current technology, all quizzes have been transitioned into text messages. To address gaps in research, a specific reward paradigm was created based on the concept of “streaks,” or reward for consecutive days of engagement in the application. Those with the longest “streak” will be placed in a drawing for an extra cash prize of \$10 every two weeks.

3.2.3 Phase 2

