This phase will start at their next visit with their diabetes provider, which usually occurs after 3 months +/- 1 month. During this phase, control group will continue to not receive text messages, and intervention group will continue to receive text messages. HbA1c and diabetes treatment plan will be collected from the medical record. SCI will be completed at this time. All subjects will get \$10 for completing the second SCI. Invitation to fill out second SCI will be administered via text message. If second SCI is not filled out 7 days after this invitation, a reminder text message will be sent. If not filled out 7 days after reminder text message, a second reminder text message will be sent. No further reminders for that SCI will be sent.

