6.2 Secondary Endpoints

Secondary endpoints will include the following:

- The change in HbA1C score during the intervention phase.
- Measure the response rate to text messages in the context of the incentivized reward program
- Responses to the intervention assessment questionnaire.
- Durability analysis of adherence to text message intervention from visit 2 to 3.
- Mean SCI score and HbA1C changes from visit 1 to visit 3 and visit 2 to visit 3.

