7.1.1 Treatment Compliance and Adherence

Compliance for the intervention arm will be measured on a bi-weekly basis. Once every two weeks, the MyDiaText website will create a report showing which subjects answered text messages for the most days in a row, and randomly pick one to win a cash prize. Subjects who do not answer any text messages will not be eligible for the bi-weekly cash prize, but will still be able to be reimbursed for completion of SCI.

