9.1.2 Blinding

Given the nature of the intervention, subjects will not be blinded. All study personnel and diabetes providers will not be blinded to current subject phase during the study.

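### Discretionary discontinuation for not adhering to the texts can fall only on the intervention arm, so it can inflate the adherence endpoints and tilt the arm comparison

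*Combined protocol and SAP*

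**What the plan says.** Section 4.5 (Subject Completion/Withdrawal) reads: "They may also be discontinued from the study at the discretion of the Investigator for lack of adherence to study treatment or visit schedules". Removal here is from the study, not only from the texts, and no threshold for poor adherence is given. The same section also lets the investigator withdraw subjects who breach the study plan.

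Other sections show whom the treatment-adherence ground can reach:

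- Section 3.2.2 (Phase 1): "Subjects in the intervention group will be instructed to respond to each text as a proxy for having read it".
- Section 3.2.3 (Phase 2): "control group will continue to not receive text messages, and intervention group will continue to receive text messages".
- Section 7.1.1: "Compliance for the intervention arm will be measured on a bi-weekly basis". On payment linked to the SCI, the same section says: "Subjects who do not answer any text messages will not be eligible for the bi-weekly cash prize, but will still be able to be reimbursed".
- Section 9.1.2: "All study personnel and diabetes providers will not be blinded to current subject phase during the study".

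Section 6.2 lists two adherence endpoints, "Measure the response rate to text messages in the context of the incentivized reward program" and "Durability analysis of adherence to text message intervention from visit 2 to 3", with no denominator for either. Section 6.3.2 limits the primary analysis to randomised subjects who have an HbA1c at Visit 2. Section 4.5.1 gives subjects who withdraw the Visit 3 procedures as an early termination visit. There is no intention-to-treat statement, missing-data rule or sensitivity analysis.

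**The concern.** Adherence to the texts is both an outcome and a possible reason for leaving the study. A removed non-responder generates no further unanswered texts. One removed before Visit 2 contributes nothing to the Visit 2 to 3 durability endpoint. Poor values of these endpoints can therefore lead to exclusion from them.

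The second risk is to the randomised comparison. Controls have no texts to answer, so this ground cannot remove a control. If subjects who disengage from the texts also do worse on SCI or HbA1c, removing them leaves a selected intervention arm against an unselected control arm.

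**Working it through.** **Plan figures.** The documents give no discontinuation rate, response rate or adherence–outcome correlation, so there is no plan figure to reproduce on this point. The one related figure is the 164 subjects in 6.4 (difference 1%, SD 2.26%, two-sided alpha 0.05, power 80%). A parallel two-sample t-test gives 81.15, rounded up to 82 per arm, or 164 in total. The point does not depend on it. It does show that lost power is the lesser issue: by normal approximation, power is 0.879 with 100 against 100, 0.839 with 100 against 80, and 0.810 with 100 against 70.

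**Response rate.** Assumptions:
- one text a day for 180 days (the nominal duration in 3.4.1);
- engaged subjects answer 75% of texts and disengaged subjects 10%;
- a share p of the intervention arm is disengaged, and all of them are removed on day t.

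Formulas:
- All scheduled days: 0.75(1 − p) + 0.10p.
- Texts sent up to removal: [0.10·p·t + 0.75·(1 − p)·180] / [p·t + (1 − p)·180].
- All texts of removed subjects dropped: 0.75.

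Example, p = 0.1 and t = 30: (0.3 + 121.5)/(3 + 162) = 121.8/165 = 73.8%, against 67.5 + 1.0 = 68.5%.

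| p | All scheduled days | Removed day 90 | Removed day 30 | All their texts dropped |
|---|---|---|---|---|
| 0.1 | 68.5% | 71.6% (+3.1) | 73.8% (+5.3) | 75% (+6.5) |
| 0.2 | 62.0% | 67.8% (+5.8) | 72.4% (+10.4) | 75% (+13.0) |
| 0.3 | 55.5% | 63.5% (+8.0) | 70.7% (+15.2) | 75% (+19.5) |

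If durability were measured as the response rate over days 91–180, subjects removed by day 90 would have no days in that window, and the last column would apply to that endpoint.

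**Arm comparison.** Suppose there is no true effect, a share p of the intervention arm is removed without a usable outcome, and their mean change is worse than the rest by d. The full-arm mean is then worse than the mean of those remaining by p × d, which is the bias in favour of the texts. For HbA1c, p = 0.2 and d = 0.5 give 0.10 points; p = 0.3 and d = 1.0 give 0.30 points.

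**A second model.** Remove the least adherent share p of a normal adherence scale that correlates rho with the outcome change, starting from 100 per arm. With z the p-quantile and m = φ(z)/(1 − p), the bias is rho × m, in SDs of change. For p = 0.2, m = 0.35, so rho from 0.1 to 0.5 gives a bias of 0.035 to 0.175 SD and a type I error of 0.056 to 0.225. Over p from 5% to 30% and the same rho, bias runs from 0.011 to 0.248 SD and type I error from 0.051 to 0.381. With everyone kept and followed, selection bias is 0 and type I error is 0.05.

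**The case against.** Several points on the other side stand.

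- The rule is permissive. A reader might infer that the clause does inflate the endpoints and does tilt the comparison. The documents support only that it can: they give no threshold and no expected frequency.
- The same sentence also covers missed visits, which can happen in either arm. Only the treatment-adherence ground is one-sided.
- The 6.3.2 analysis set has no adherence exclusion. A subject discontinued after Visit 2 stays in the Visit 1 to 2 comparisons. Bias there needs removal before Visit 2 and no Visit 2 HbA1c, and HbA1c is a routine three-monthly value (5.3.1) available in the medical record (3.2.3).
- The early termination visit in 4.5.1 may recover some outcomes. This is a partial remedy: it is worded for subjects who withdraw, does not clearly cover those discontinued by the investigator, and has no rule for using its data. It cannot restore unsent texts to a denominator.
- A reader might take 7.1.1 as a flat contradiction of 4.5. It deals with prize eligibility and payment, and a silent subject could remain payable until discontinued. The sections sit uneasily together and need reconciling, but they are not opposites.
- A reader might also expect clinics to apply the rule differently. The documents do not establish that: the sites belong to one institution, adherence reports come from one system (4.3.4), and oversight rests with the PI and lead investigator (9.4.1).

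**Conclusion.** The concern holds as a route to bias of unknown frequency. Unblinded staff may remove intervention subjects on a ground that cannot apply to controls. That ground is also an endpoint, and nothing in the analysis plan guards against the effect.

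Under the assumed 75% and 10% response rates, with 10–30% removed, response-rate inflation is about 3 to 8 points for removal at day 90 and 5 to 15 points at day 30. The figure of 6.5 to 19.5 points is a ceiling, not an estimate, because it requires every text of the removed subjects to be discarded. This inflation needs no link between adherence and outcome.

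The arm bias of about p × d does need such a link, and it applies to the Visit 1 to 2 comparisons only for subjects removed before Visit 2 without that HbA1c. Later removal can affect the Visit 3 comparisons. At 5–10% removed with a weak correlation (0.1) it is small: 0.01 to 0.02 SD, with type I error of 0.051 to 0.052. The upper illustration, d = 1.0, equals the whole design difference in 6.4 and has no support in the documents.

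**What to change.** - **Section 4.5.** State that not answering texts, including when treated as a breach of the study plan, is not a ground for ending outcome follow-up. State that Visit 2 and Visit 3 HbA1c and SCI are collected for all randomised subjects unless consent is withdrawn. Whether texts continue to a non-responder is left to the sponsor.
- **Sections 4.5, 4.5.1 and 7.1.1.** Reconcile them. Say whether the early termination visit covers subjects discontinued by the investigator and how its data enter the analysis.
- **Section 6.3.2.** Analyse all randomised subjects with outcome data as assigned, whatever their adherence or discontinuation of texts. Report discontinuations and reasons by arm.
- **Section 6.2.** Compute response rate over all subjects randomised to the intervention, for the scheduled period from randomisation. Compute durability over the Visit 2 to Visit 3 period. Where a visit date is missing, use a fixed nominal window, for example days 1–180 and 91–180. Count days after a subject stops as non-response. Because that is a choice of estimand, add a messages-sent denominator as a sensitivity analysis.

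The cost is a few sentences, a lower reported response rate, and slightly more follow-up and analysis work. The extra burden is small because HbA1c comes from routine visits and SCI invitations go out by text.

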4.5.1 Early Termination Study Visit

Subjects who withdraw from the study will have all procedures enumerated for Visit 3 as the early termination visit. Should they withdraw by sending a text message to the text message carrier "STOP," a one-time e-mail will be sent from study personnel to the address provided at registration with visit 3 procedures.

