5.3 Efficacy Evaluations

5.3.1 Diagnostic Tests, Scales, Measures, etc.

The efficacy of this intervention in improving glycemic control will be determined using HbA1c values. HbA1c is checked every 3 months as part of the diabetes treatment plan. These values will be collected as a research lab at each visit.

The efficacy of this intervention in improving diabetes self-management skills will be determined by the SCI questionnaire. This will be completed at each study visit.

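### Subjects who leave early get at most an untimed early termination assessment, and nothing provides for collecting their outcomes at the Visit 2 and Visit 3 windows

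*Combined protocol and SAP*

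**What the plan says.** All places are in the combined protocol and SAP.

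- **Leaving the study (4.5, 4.5.1).** A subject may withdraw at any time. The investigator may also discontinue a subject, for example for poor adherence to study treatment or to the visit schedule. Section 4.5.1 then says: "Subjects who withdraw from the study will have all procedures enumerated for Visit 3 as the early termination visit". For those who withdraw by texting STOP, "a one-time e-mail will be sent from study personnel to the address provided at registration with visit 3 procedures". No day or window is given.
- **Visit 3 procedures (4.3.3).** Medical record review, "Lab: hemoglobin A1c", the SCI and the exit questionnaire.
- **How they are obtained.** Under 3.2.4, HbA1c comes from the medical record, and the questionnaires are invited by text with up to two reminders. Section 5.2.1 lists the most recent HbA1c on file. Section 5.3.1 says "HbA1c is checked every 3 months as part of the diabetes treatment plan" but also describes the values as a research lab.
- **Unscheduled visits (4.4).** "Since study visits will coincide with visits with primary diabetes provider, no unscheduled visits will take place". Subjects seen too soon after the last visit are not approached: "If a subject is seen by their diabetes provider or care team less than 2 months from the previous visit" is the condition.
- **Analysis (6.1 to 6.3.2).** The SCI and HbA1c comparisons are built on Visits 1, 2 and 3. The primary analysis set is the randomized subjects with an HbA1c at Visit 2. Section 6 does not say whether an early termination value counts as Visit 2, Visit 3 or neither.

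**The concern.** There are two problems, and the second matters more.

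First, 4.5.1 and 4.4 pull against each other. Withdrawal can happen on any day, yet study contact is tied to routine provider visits. If the early termination visit means attendance between those visits, both sections cannot be followed.

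Second, the plan treats leaving as the end of outcome collection. A subject who goes before Visit 2 has no planned Visit 2 SCI or HbA1c and so drops out of the primary set. The same subject is probably still attending the same clinic and having HbA1c measured about every 3 months.

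The loss need not be balanced. Controls receive SCI invitations by text and could also reply STOP, but only the intervention arm gets daily messages and has a text treatment to fail to adhere to. A complete-case comparison would then set all controls who stay against a more selected intervention group. If an exit value were instead entered as Visit 3, the 6-month comparison would contain values from other times.

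**Working it through.** **1. Do the sections conflict?**

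| Situation on leaving | 4.5.1 | 4.4 | Compatible? |
|---|---|---|---|
| Routine provider visit at least 2 months after the last | Visit 3 procedures | Allowed | Yes |
| Between routine visits, in person | Visit 3 procedures | No unscheduled visits | No |
| Provider visit under 2 months after the last | Visit 3 procedures | Subject not approached | No |
| Remote questionnaires and chart review only | Most Visit 3 items | Not addressed | Yes, if HbA1c is a chart value |

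The conflict is real but conditional.

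**2. How often would an exit date fall outside both windows?** The documents give Visit 2 at 3 months +/- 1 month, and Visit 3 a further 3 months +/- 1 month later. My assumptions are 30-day months, a withdrawal day spread evenly over the study, assessment on that day, and Visit 3 at 90 days after Visit 2.

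- Visit 2 on day 90: days 1 to 59 and 91 to 149 fall in neither window. 59 + 59 = 118 of 179 days, or 66%.
- Visit 2 on day 60: 118 / 149 = 79%.
- Visit 2 on day 120: 118 / 209 = 56%.
- Most lenient reading, any day from 60 to 240 counts: 59 / 179 = 33%.

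So between a third and four fifths of possible exit days would give a value that is neither a 3-month nor a 6-month outcome.

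**3. What if the exit value were used as Visit 3?** With no clinic HbA1c since baseline, the most recent value on file is the Visit 1 value, so the recorded change is zero. Let a fraction p of the intervention arm carry such a value. Suppose the true effect is 1 point (the difference used in 6.4), the same for leavers, with no change in controls:

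observed effect = (1 - p) x 1 + p x 0 = 1 - p

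- p = 10%: 0.90
- p = 20%: 0.80

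The documents state neither p nor that such values would be used.

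**4. Is it a power problem?** Section 6.4 gives 164 subjects for a 1-point difference, SD 2.26, alpha 0.05 and 80% power. The two-sided normal formula gives 2 x (1.960 + 0.842)^2 x 2.26^2 / 1^2 = 80.2, so 81 per arm. The two-sample t calculation gives 81.15, so 82 per arm and 164 in total, as stated. Recruiting 200 allows a loss of 1 - 164/200 = 18%. On those inputs, losing 10% leaves 84% power and losing 25% leaves 77%. This concerns HbA1c only; there is no calculation for SCI, which 6.1 names as primary. Moderate loss is therefore mainly a question of who is missing from each arm.

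**The case against.** A reader might infer more than the documents support. Five stronger readings do not stand.

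- **That the assessment must take place on the day of leaving.** Section 4.5.1 gives no timing. That silence is the defect.
- **That 4.4 makes the assessment impossible.** It permits collection at a routine visit at least 2 months after the last, and does not bar chart review or remote questionnaires.
- **That an e-mail can deliver nothing useful.** The SCI and exit questionnaire are already completed remotely, and 3.2.4 takes HbA1c from the record. Only a fresh sample, as the research-lab wording of 5.3.1 implies, could not come that way.
- **That the assessment serves no endpoint.** Section 6.2 lists responses to the intervention assessment questionnaire, with no visit attached.
- **That everyone who leaves is lost at both time points.** Someone who leaves on day 120 after a day-90 Visit 2 keeps the Visit 2 outcome.

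It is also fair to say that 4.5.1 already names a separate early termination visit and never equates it with Visit 3 for analysis, and that the Visit 3 comparisons are secondary in section 6. Further follow-up of people who have left depends on consent wording that is not available here.

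What remains is the missing timing, the missing analysis rule, the conditional conflict with 4.4, and above all the lack of any provision to collect window outcomes from people who stop the texts or are discontinued.

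**Conclusion.** The point holds as a cheap improvement. Subjects who leave before Visit 2 fall out of the primary set under the plan as written, and the loss can differ by arm. Sections 4.5.1 and 4.4 must be reconciled for exits between routine visits.

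No size can be put on the bias, because the documents give no dropout rate, withdrawal timing or rule for using exit values. The 0.90 and 0.80 figures illustrate one mechanism: baseline values carried into Visit 3 in the intervention arm, with no change in controls. The 33% to 79% range depends on evenly spread withdrawal days and same-day assessment. Neither is a forecast. The documents do not show that exit values will be analysed as Visit 3, only that nothing prevents it.

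**What to change.** 1. Reconcile 4.5.1 with 4.4, stating when and how the early termination assessment is made and whether 4.5.1 also covers subjects discontinued by the investigator.
2. Separate stopping the texts from withdrawing consent for data collection. Suggested wording: *Unless consent for data collection is withdrawn, subjects who stop the text messages or are discontinued have HbA1c taken from the routine medical record and are sent the SCI link (by e-mail if texts are refused) at the original Visit 2 and Visit 3 windows.*
3. Add to section 6: *Any assessment made on leaving is dated, labelled Early Termination, and not used as Visit 2 or Visit 3 unless it falls in that window.*

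The cost is protocol wording, one visit label in the database, and a few chart look-ups and e-mails for each subject who leaves. The single e-mail after STOP would become up to two SCI links. The consent wording must permit continued record access and should be checked before the change is made.
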